3.1.2 Secondary Objectives

Secondary objectives are determination of responder rates to clinical endpoints and mean change in physiologic endpoints.

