1 SCHEDULE OF VISITS

Treatment/Control Group Subjects:

Procedure / Assessment	Baseline	Randomization	Treatment (Tx) 1*	Treatment (Tx) 2 ⁺⁺⁺	12 Month post treatment Follow-Up Visit ⁺⁺⁺	36 Months post treatment Follow-Up Visit ⁺⁺⁺
Informed Consent	X					
Baseline Assessment ¹	X					
Randomization	X	X				
Procedure Treatment	X		X	X		
Medications	X		X	X	X	X
AEs			X	X	X	X
PFTs including Lung volumes and Spirometry	X				X	X
6MWT	X					
QOL (SGRQ, mMRC, CAT, EQ5D)	X					
HRCT (inspiratory and Expiratory)	X				X	X
Chest X-Ray	X		X ²	X ²		
Pregnancy test	X		X	X		

¹Includes demographics, medical history, physical exam, vitals, echocardiogram, and additional pre -treatment evaluations (e.g. blood panel, blood gas).

²At procedure visits, a Chest X-Ray or a still fluoroscopic image will be performed immediately post procedure. A second chest X-Ray should be done before discharge, a minimum of 4 hours following the first chest X-Ray.

*No more than 45 days post baseline visit

⁺⁺⁺ 2 months ±4 weeks post initial coil treatment

⁺⁺⁺ ±4 week

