3.2 Trial Design

This is a prospective, multicenter, open label, randomized (2:1), controlled study comparing outcomes in subjects treated with the Coil System (Treatment) to a medically-managed control group (Control). Control group patients will be eligible for treatment with Coils (Crossover) 6 months after entry into the study.

The study is anticipated to begin enrollment early 2018. All subjects randomized to Treatment will be followed for 36 months post initial treatment. Subjects randomized to Control will be eligible for crossover as soon as possible. Crossover subjects will then be followed for 36 months post initial treatment. The anticipated last patient visit is expected in first half of 2023. If Control subjects choose not to crossover to treatment, they will exit the study immediately.

The data in this study, including Subject characteristics, outcome measures (e.g., health-related QOL, pulmonary function, exercise capacity), and safety (SAEs and specific respiratory AEs of interest), will be collected via the use of an electronic data capture (EDC) system on electronic Case Report Forms (eCRFs).

No biological samples will be taken other than blood draws taken at screening, and no biological samples will be stored for the study.

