6.4.3 Follow-Up Visits

Follow-up office visits will be conducted at 12, and 36 months post first Endobronchial Coil treatment for both Treatment group subjects and Crossover subjects..

Follow-up visits should be conducted per the schedule below. Study specific follow-up visits should take place during exacerbation free periods defined as 30 days with symptoms within normal day to day variability.

12- and 36-month study follow-up visits will include:

- PFT
- AE review
- Medications
- Inspiratory and expiratory HRCT

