6.5.6 Six Minute Walk Test

6MWT will be conducted by a qualified individual according to ATS/ERS Guidelines as specified in the schedule of visits.

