6.5.13 Quality of Life

QoL instruments suitable for Subjects being treated for emphysema (i.e., SGRQ, CAT, EQ5D, and mMRC) will be administered at study visits as specified in the schedule of visits.

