9 DATA MANAGEMENT

Data from the study will be collected via EDC. Clinical data will be sent in a secured validated format to Boston Scientific Corporation on an ongoing basis.

Data will be entered in the eCRFs at the study site. Trained study personnel will be responsible for entering data on the observations, tests and assessments specified in the protocol into the eCRF system and according to the eCRF instructions. The eCRF instructions will also provide the study site with data entry instructions. Risk-based monitoring of investigational site(s) will be conducted. Data entered in the eCRF will be immediately saved to a central database and changes tracked to provide an audit trail. When data have been entered, reviewed, edited and Source Data Verification (SDV) performed as specified per the clinical monitoring plan, the investigator will be required to sign the eCRF electronically as per the agreed upon project process, and data will be locked to prevent further editing. A copy of the eCRF will be archived at the study site at the end of the study.

Data verification and data validation checks will be performed by Boston Scientific Corporation Data Management or designee utilizing electronic edit checks comprised of validated computer programs and manual data review. Any data discrepancies will be referred back to the investigator. After the database has been declared clean it will be locked, and editing in the database will only be allowed with the proper documentation.

After database lock, data will be extracted to SAS® (SAS Institute, Inc., Cary, NC, USA) for analysis as defined in the SAP.

AEs will be coded according to the version of MedDRA agreed upon by Boston Scientific Corporation.

Electronic data checks for accuracy will be built into the EDC system. Data analyses will be performed and reviewed in an aggregate and de-identified fashion. These reviews will aid in continued refinement of the data collection process and analysis. Access to de-identified data will be provided to Boston Scientific Corporation .

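### The visit schedule has no post-baseline 6MWT, CAT, mMRC or EQ-5D, so the secondary responder objective can be met only on lung function unless unlisted 6-month data exist

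*Combined protocol and SAP*

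**What the plan says.** The secondary objective in Section 3.1.2 reads: "Secondary objectives are determination of responder rates to clinical endpoints and mean change in physiologic endpoints". It names neither the endpoints nor a responder threshold. Section 3.2 says that the data to be collected include "outcome measures (e.g., health-related QOL, pulmonary function, exercise capacity". Section 8.5 analyses effectiveness through a 6-month visit and adds descriptive summaries of effectiveness endpoints at 12, 24 and 36 months.

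Timing of the measures is left to the schedule. Section 6.5.6 says "6MWT will be conducted by a qualified individual according to ATS/ERS Guidelines as specified in the schedule of visits", and Section 6.5.13 says that the quality-of-life instruments "will be administered at study visits as specified in the schedule of visits". In that schedule (Section 1), the 6MWT row and the row "QOL (SGRQ, mMRC, CAT, EQ5D" are marked at baseline only. The row "PFTs including Lung volumes and Spirometry" is marked at baseline, 12 months and 36 months.

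Section 6.4.3 says "Follow-up office visits will be conducted at 12, and 36 months post first Endobronchial Coil treatment" and lists lung function, adverse-event review, medications and HRCT as the content of those visits. The synopsis gives the same list.

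**The concern.** A responder rate, like a mean change, needs a value after baseline. If the plan is followed as written, 6MWD, CAT, mMRC and EQ-5D have none. Yet the synopsis describes the device as indicated to improve three things: quality of life, lung function and exercise capacity. On this schedule exercise capacity gets no post-treatment result, and CAT, mMRC and EQ-5D serve only to describe the population at entry. A reader of Sections 3.1.2, 3.2 and 8.5 would expect results that the scheduled visits cannot supply.

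**Working it through.** The plan gives no figure to reproduce here; the check is a count of scheduled assessments against stated purposes.

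**Step 1: what a responder rate needs.** For subject i, measure Y and visit t, the subject is a responder if the change Y_i(t) − Y_i(0), taken in the direction of benefit, reaches a cut-off c. This requires a baseline value, a value at t, and c.

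**Step 2: what is scheduled** (Section 1, checked against the synopsis and Section 6.4.3).

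| Measure | Baseline | 6 mo | 12 mo | 24 mo | 36 mo | Post-baseline values scheduled |
|---|---|---|---|---|---|---|
| 6MWT | yes | no visit listed | no | no visit listed | no | 0 |
| CAT, mMRC, EQ-5D (same row as SGRQ) | yes | no visit listed | no | no visit listed | no | 0 |
| PFT (spirometry, lung volumes) | yes | no visit listed | yes | no visit listed | yes | 2 |

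Four measures at two scheduled follow-up visits make 4 × 2 = 8 possible measure-by-visit results, of which 0 are planned. The two written visit lists agree with the grid, so a mark lost from the table is an unlikely explanation.

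**Step 3: what the objectives call for.**

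- Section 3.1.2, responder rates: no cut-off c appears in Section 3 or Section 8, and Section 8 contains no responder analysis. On 6MWD, CAT, mMRC and EQ-5D the follow-up value is missing as well. On FEV1 and RV the values exist at 12 and 36 months, and only c is missing.
- Section 3.1.2, mean change in physiologic endpoints: obtainable from lung function at 12 and 36 months.
- Section 3.2, exercise capacity as an outcome: measured at baseline only.
- Section 8.5, summaries at three time points (12, 24, 36 months): two of the three have a visit, and 24 months has none.

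**Step 4: who contributes at 12 and 36 months.** Sections 4.3 and 5.1.4 have controls either cross over to coils or leave the study at once. Section 8.5 accordingly summarises FEV1 at 12 and 36 months for all coil-treated subjects. Responder rates at those visits therefore have no concurrent control. Only the 6-month comparison of the 80 Treatment and 40 Control subjects (80 + 40 = 120) is randomised.

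**Step 5: the 6-month visit.** Section 3.4 sets both co-primary endpoints at 6 months, Section 6.2 has the core laboratory review 6-month lung function, and Section 8.5 analyses effectiveness through that visit. Between them these sections place FEV1 and SGRQ at 6 months. None places 6MWT, CAT, mMRC or EQ-5D there, and none excludes them.

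**The case against.** The strongest reply is that the objective is not lost. Section 3.1.2 does not say which clinical endpoints it means, so treating 6MWD, CAT, mMRC and EQ-5D as the responder measures is partly inference. The physiologic half is covered by lung function at 12 and 36 months, and an FEV1 or RV responder rate needs only a threshold. Sections 3.3 and 8.1 report randomisation in the past tense, so a 6-month visit may already have taken place under earlier protocol text, with these measures included. Section 8.2 also puts detailed methods in a separate SAP, which may define responders.

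Most of this stands, and it limits the point. A reader might infer that the secondary objective cannot be answered at all, or that none of the 120 subjects has a usable value on these measures. The documents do not support either statement: lung-function data are scheduled, and what was done at 6 months is unstated. What does not stand is the appeal to the SAP. It can supply a cut-off, but not measurements that no listed visit collects.

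A reader might also take the remark in Section 9, "These reviews will aid in continued refinement of the data collection process and analysis", as permission to choose cut-offs after seeing results. The passage concerns aggregate, de-identified data review and mentions neither endpoints nor thresholds, so it cannot carry that reading. Nor would a calculation of how often cut-off selection exaggerates a difference between 80 and 40 subjects apply at 12 and 36 months, where no randomised comparison remains.

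**Conclusion.** The point holds as a mismatch between objectives and schedule. From the assessments this protocol schedules, no responder rate or change can be obtained on 6MWD, CAT, mMRC or EQ-5D (0 planned post-baseline values on each), exercise capacity has no planned post-treatment result, and the 24-month summaries have no visit behind them. FEV1 and RV responder rates and mean changes are obtainable at 12 and 36 months in coil-treated subjects, uncontrolled.

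This rests on reading the schedule as the complete list of study assessments, which Sections 6.5.6 and 6.5.13 invite. If the four measures were taken at an unlisted 6-month visit, the fault is in the schedule and the randomised comparison can be recovered. If they were not, the objective as worded claims more than the trial measures. The documents do not settle which applies. The absence of a responder threshold would by itself be a missing detail; the absence of measurements limits what the trial can conclude.

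**What to change.** 1. State which assessments were made at 6 months. If 6MWT and the quality-of-life instruments were collected, restore that visit and its content to Section 1 and Section 6.4.3, and base the secondary responder rates on it. This costs text only, and it preserves the one randomised comparison.
2. If they were not collected, choose one of two courses:
   - Add CAT, mMRC and EQ-5D to the existing 12- and 36-month visits. The cost is an amendment and a few minutes per visit, and the results will be open-label and uncontrolled.
   - Narrow Section 3.1.2 to FEV1 and RV responder rates (keeping mean change in physiologic endpoints), delete exercise capacity from Section 3.2, and state that no post-treatment exercise result will be reported. The cost is an openly smaller claim.
3. On the narrowing course, also remove 24 months from Section 8.5. On any other course, reconcile that time point with the schedule.
4. In Section 8 or the SAP, fix one responder cut-off for each retained measure before any responder table is run. Count a missing value as non-response only where the assessment was scheduled for that subject, so that anyone whose visit came before an amendment is not misclassified.

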3.2 Trial Design

This is a prospective, multicenter, open label, randomized (2:1), controlled study comparing outcomes in subjects treated with the Coil System (Treatment) to a medically-managed control group (Control). Control group patients will be eligible for treatment with Coils (Crossover) 6 months after entry into the study.

The study is anticipated to begin enrollment early 2018. All subjects randomized to Treatment will be followed for 36 months post initial treatment. Subjects randomized to Control will be eligible for crossover as soon as possible. Crossover subjects will then be followed for 36 months post initial treatment. The anticipated last patient visit is expected in first half of 2023. If Control subjects choose not to crossover to treatment, they will exit the study immediately.

The data in this study, including Subject characteristics, outcome measures (e.g., health-related QOL, pulmonary function, exercise capacity), and safety (SAEs and specific respiratory AEs of interest), will be collected via the use of an electronic data capture (EDC) system on electronic Case Report Forms (eCRFs).

No biological samples will be taken other than blood draws taken at screening, and no biological samples will be stored for the study.

3.3 Randomization

A total of 120 subjects were randomized in a 2:1 ratio of Treatment to Control respectively (80 Treatment group subjects, 40 Control group subjects) across up to 30 sites.

3.4 Primary Endpoint (s)

The Co-Primary Effectiveness Endpoint for the study is:

- Percent change in FEV₁ from baseline to 6 months
- Change in St. George's Respiratory Questionnaire (SGRQ) from baseline to 6 months.

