
Visits and Assessments:
	
Baseline Visit:
 
After obtaining Subject consent, the Subject’s eligibility for Treatment was evaluated. Relevant medical history, medications, comorbidities, previous treatments of emphysema, physical activity / rehabilitation status, and baseline characteristics were collected and entered into the Electronic Data Capture (EDC) system. Pulmonary Function Test (PFT), pregnancy test, imaging (HRCT scan inspiratory and expiratory,), exercise testing (6 Minute Walk Test – 6MWT), dyspnea assessment (mMRC), quality of life (QoL) assessment (St Georges Respiratory Questionnaire (SGRQ), COPD Assessment Test (CAT), EuroQoL-5 Dimensions QoL questionnaire (EQ-5D), and blood gases (BG) were collected. Eligibility was reviewed by the ERC, and if deemed eligible, subject was randomized.
 
Procedure Visits:
 
Subjects will undergo the Coil treatment. One lung will be treated per procedure, with procedures separated by approximately 2 months. Lobar targeting will be based on quantitative CT (QCT) densitometry analysis and Coils will be placed in the lobe with the higher LAA as measured in Hounsfield units (HU) at a -950 HU threshold.

Procedure data, chest X-ray data, adverse event data, pregnancy test, and medications will be collected and entered into the EDC system.

Each center’s principal investigator (PI), or one primary implanter, will perform all coil treatments in ELEVATE. If necessary, a secondary implanter will also be trained as a back-up.

Follow-up Visits:

Follow-up visits should be conducted per the schedule below. Study specific follow-up visits should take place during exacerbation free periods defined as 30 days with symptoms within normal day-to-day variability.

12- and 36-month study follow-up visits will include:

- PFT
- AE review
- Medications
- Inspiratory and expiratory HRCT

Definition of visit windows:

Patients should have visits scheduled during exacerbation-free periods, defined as 30 days with symptoms within normal day to day variability.

Treatment/Control Group Subjects:

Visit:	Visit Window:
Baseline	Eligibility, Inclusion
Randomization	
Treatment 1	
Treatment 2	2 months +/- 4 weeks post 1st treatment
12 months post Treatment 1	12 months +/- 4 weeks post 1st treatment
36 months post Treatment 1	36 months +/- 4 weeks post 1st treatment

Device:
	
PneumRx Endobronchial Coil System (Coil)

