	
Death, Led to serious deterioration in the health of the subject that either resulted in A life threatening illness or injury, or A permanent impairment of a body structure or a body function, or In-patient or prolonged hospitalization, or Medical or surgical intervention to prevent life-threatening illness or injury or permanent impairment to a body structure or a body function Led to fetal distress, fetal death or a congenital anomaly/birth defect.
 
Information on Specific Respiratory Events of interest will be collected and analyzed via event specific case report forms. These events of interest include:
 
 • COPD exacerbation • Hemoptysis • Pneumothorax • Lower Respiratory Tract Infection/Pneumonia • Tissue Reaction, Localized (a.k.a. Coil Associated Inflammatory Response Syndrome (CAIRS), also called Coil Associated Opacity (CAO) in the IFU)

Statistical Analyses:
	
The co-primary effectiveness endpoint will be analyzed on the intent-to-treat (ITT) population through the 6-month visit, using descriptive statistics to summarize results separately for treatment and control groups. No comparative inferential statistics will be conducted.

	
Safety analyses will be conducted on the safety population defined as those subjects who enter the bronchoscopy suit for the initial Coil

--	--

	
procedure. AE and SAEs will be summarized by Treatment group based on MedDRA codes. Incidence rates through 6 months will be summarized for treatment and control groups. Events will also be summarized by relevant, discrete time periods including the Treatment recovery period (30 days from either treatment).
 
Descriptive statistics will summarize percent change in FEV₁ as well as AEs and SAEs at 12 and 36 months follow-up for all coil treated subjects.

RESULTS	

Number of subjects to be analyzed
	
A total of 120 Subjects were randomized in a 2:1 ratio of Treatment to Control, respectively (80 Treatment group subjects, 40 Control group subjects).

Duration of the follow-up	Subjects will continue in the study through 36 months from first Coil implant. If Control subjects don't participate to crossover, they will exit the study immediately.
----------------------------------	--

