5.1.3 Post-implant Management

Prophylactic regimen of medications should be administered according to the IFU and standard of care (SoC).

Per the IFU, a chest X-ray or still fluoroscopy image should be done post-procedure to verify Coil placement and to ensure there is no pneumothorax. A second, confirmatory chest X-ray should be done before discharge a minimum of 4 hours following the first chest X-ray. The second, confirmatory X-ray must be two views, posterior anterior (PA) and Lateral.

The Subject will be counseled on expected side-effects of the Coil procedure, including the potential AEs listed in Section 7.7. The Subject will be instructed to contact the treating physician immediately should any of the potential AEs be experienced. It is particularly important that Subjects be instructed at discharge to contact their implanting physician if they experience symptoms that may be indicative of pneumonia or CAIRS/CAO, to ensure that appropriate treatment is delivered.

Follow-up visits should be conducted per the schedule below. Study specific follow -up visits should take place during exacerbation free periods defined as 30 days with symptoms within normal day to day variability.

Treatment Group Subjects:

Visit	Visit window
Baseline visit	Eligibility, inclusion
Randomization	
First coil treatment	No more than 45 days post baseline visit
Second coil treatment	2 months +/- 4 weeks post first procedure
12-month follow-up	12 months +/- 4 weeks post first procedure
36-month follow-up	36 months +/- 4 weeks post first procedure

Control Group Subjects:

Visit	Visit window
Baseline visit	Eligibility, inclusion
Randomization	
First coil treatment	
Second coil treatment	2 months +/- 4 weeks post first procedure
12-month follow-up	12 months +/- 4 weeks post first procedure
36-month follow-up	36 months +/- 4 weeks post first procedure

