8.5 Efficacy Analyses

All effectiveness analyses will be analyzed on the ITT population through the 6-month visit, using descriptive statistics to summarize results separately for treatment and control groups. No comparative inferential statistics will be conducted. In addition, descriptive statistics will summarize percent change in FEV₁ from baseline to 12 and 36 months for all coil treated subjects. Baseline will be defined as the last measurement taken prior to coil treatment.

Descriptive statistics will summarize effectiveness endpoints at 12, 24 and 36 months follow-up.

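### Both co-primary endpoints (FEV1 and SGRQ at 6 months) need a 6-month assessment that no visit list in the protocol schedules

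*Combined protocol and SAP*

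**What the plan says.** Five places call for a 6-month value:

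- The synopsis (Primary Objectives) and Section 3.4 define both co-primary endpoints at 6 months. They are percent change in FEV1 and change in the St George's "Respiratory Questionnaire (SGRQ) from baseline to 6 months".
- The synopsis (Statistical Analyses) states: "The co-primary effectiveness endpoint will be analyzed on the intent-to-treat (ITT) population through the 6-month visit".
- Section 8.5 states: "All effectiveness analyses will be analyzed on the ITT population through the 6-month visit".
- Section 6.2 has the core laboratory review lung function data from baseline and from month 6.

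The visit lists say something else:

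- The synopsis visit-window table goes from the second treatment to "12 months +/- 4 weeks post 1st treatment", then to 36 months.
- The Section 1 schedule has columns for baseline, randomization, two treatments, 12 months and 36 months. The row that begins "QOL (SGRQ, mMRC, CAT, EQ5D" is marked at baseline only.
- The Treatment and Control tables in Section 5.1.3 both go from the second coil treatment to "12 months +/- 4 weeks post first procedure", then to 36 months.
- Section 6.4.3 states: "Follow-up office visits will be conducted at 12, and 36 months post first Endobronchial Coil treatment for both Treatment group subjects and Crossover subjects". Its visit contents are lung function, adverse events, medications and CT, without SGRQ.

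Section 6.5.13 sets no timing of its own for the quality-of-life instruments. They "will be administered at study visits as specified in the schedule of visits".

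**The concern.** A primary endpoint needs a scheduled measurement at its time point. Here a site that follows the visit lists would collect no SGRQ after baseline at any time, and no FEV1 near 6 months. Control subjects are the clearest case. Their table in Section 5.1.3 goes straight from randomization to first coil treatment, and every later visit is counted from that treatment. Yet Section 8.3 puts all randomized subjects in the ITT population, and Section 8.5 summarizes the two groups separately.

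At stake is whether the two 6-month values exist for both arms, under what window they were obtained, and from what starting date the 6 months run. The text states none of these.

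Three nearby passages also fail to line up:

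- Section 6.5.5 speaks of lung function quality assurance at baseline, whereas Section 6.2 covers baseline and month 6.
- The last sentence of Section 8.5 names a 24-month summary, for which there is no visit.
- Crossover is placed 6 months after entry in some passages and without delay in others.

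**Working it through.** **1. Plan's own figure.** The plan gives 120 subjects, 80 Treatment and 40 Control, in a 2:1 ratio. The arithmetic agrees: 80 + 40 = 120 and 80/40 = 2. No alpha, power, effect size or SD is given, so 120 cannot be derived. The point does not depend on it.

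**2. Visit lists against the endpoint.**

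| List | Post-baseline visits | 6-month entry | SGRQ after baseline |
|---|---|---|---|
| Synopsis windows | Treatments 1 and 2, 12 and 36 months | none | not listed |
| Section 1 | same | none | no mark |
| 5.1.3 Treatment | same | none | not listed |
| 5.1.3 Control | same | none | not listed |
| 6.4.3 | 12 and 36 months | none | not in visit contents |

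Lists with a 6-month entry: 0 of 5. The short list of 12- and 36-month visit contents in the synopsis could be counted as a sixth; it has none either. In Section 1, lung function has 3 marks (baseline, 12 and 36 months), so 2 are post-baseline. The quality-of-life row has 1 mark, so 0 are post-baseline.

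**3. Could a visit window reach month 6?** Take one month as 365.25/12 = 30.4375 days and 4 weeks as 28 days, counting from first treatment.

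- Treatment 2: 2 × 30.4375 ± 28 = 60.9 ± 28, day 32.9 to 88.9.
- 12 months: 365.25 ± 28, day 337.25 to 393.25.
- 36 months: 1095.75 ± 28, day 1067.75 to 1123.75.
- Month 6: 6 × 30.4375 = day 182.6.

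Month 6 falls 182.625 − 88.875 = 93.75 days after the latest second treatment and 337.25 − 182.625 = 154.6 days before the earliest 12-month visit. No window covers it.

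The endpoint does not say when its clock starts. If it starts at baseline, and first treatment follows by at most 45 days (Section 1; Treatment table in 5.1.3), month 6 falls between day 182.625 − 45 = 137.6 and day 182.6 after first treatment. That is still outside every window. The second treatment visit includes neither lung function nor SGRQ in any case.

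**4. Untreated Control subjects.** Every visit after randomization is a coil treatment or is counted from one. Scheduled post-baseline assessments without treatment: 0.

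**5. Signs of when the text was written.** Five places report in the past tense that 120 subjects were randomized: synopsis, 3.3, 6.1, 6.5.10 and 8.1. Section 6.4.2 has subjects of either arm undergo coil treatment. Sections 6.2 and 8.5 still use the future tense for the 6-month review and analysis.

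**6. Crossover timing.** Two statements say 6 months: synopsis Design and Section 3.2, first paragraph. Four say as soon as possible or immediately: synopsis Timelines, Section 3.2 second paragraph, 4.3 and 5.1.4.

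**The case against.** The strongest reply is that this is a late amendment. Randomization is reported as done, so the 6-month visits may be complete and may have been taken out of the schedule on purpose. That is plausible, and it means the gap cannot be called an oversight. It does not remove the contradiction: the schedule still lists baseline and randomization, the analysis text still looks forward to a 6-month visit, and nothing in the text says the values were collected. Section 8.2 makes the SAP a separate document, which could not be checked, nor could the front pages. Either may supply the answer.

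A reader might also infer more than the documents support:

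- **That the 6-month safety summary depends on a 6-month visit.** It does not. The synopsis has safety information collected continuously and Section 7.2 records onset dates, so incidence through 6 months can be counted from dated events. Untreated Control subjects fall outside the Safety Population as Sections 8.3 and 8.6 define it, and adding a visit would not change that.
- **That the Per Protocol population is distorted.** Section 10.9 does make an endpoint test not done a major deviation, but no analysis in the text uses that population.
- **That one missing 6-month value makes the matter critical.** Section 4.4 foresees withdrawal and loss to follow-up, so ordinary dropout would produce that. The question is whether anyone was never asked for the assessment.
- **That the exit passages conflict.** They agree that Control subjects who do not cross over leave at once. Only the crossover timing is inconsistent.

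**Conclusion.** The contradiction holds. Five places need a 6-month assessment and 0 of 5 visit lists provide one. As written, the plan schedules no post-baseline SGRQ, no FEV1 near month 6, and nothing after baseline for an untreated Control subject.

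It should be fixed. If every subject was asked for a 6-month assessment under other instructions, the defect is an unstated data source. If some never were, the ITT summary of a co-primary endpoint has a gap built in by the schedule, which is more serious. The text does not settle which case applies and gives no count of subjects without the value. It would be wrong to conclude that data have been lost. Sections 8.5 and the synopsis rule out comparative inference, so no test or power is affected.

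The conclusion rests on the text available, without the separate SAP or the front pages. The schedule table was read by program from a PDF. The absence of a 6-month column does not depend on where the marks fall, and Section 6.4.3 independently omits SGRQ from the 12- and 36-month visits.

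**What to change.** 1. For any subject not yet at month 6, include a 6-month assessment (post-bronchodilator lung function and SGRQ) in the synopsis windows, Section 1, Section 5.1.3 and Section 6.4.3. Give a window and a stated clock start for each arm.
2. For subjects past month 6, state in Section 8.5 the protocol version and window under which the values were collected, or cross-refer to the SAP if it already says so. Report how many of the 80 Treatment and 40 Control subjects have each co-primary value.
3. Align Section 6.5.5 with Section 6.2 on which lung function tests are quality-reviewed.
4. In the last sentence of Section 8.5, reconcile the 24-month time point with the schedule and say which effectiveness endpoints are meant at 12 and 36 months. The sentences before it in that section name only FEV1 at those times.
5. Reconcile the crossover-timing statements listed in step 6 of the working. No position is taken here on the timing.

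Cost: if every subject has already been assessed at month 6, text changes and one count. Otherwise, one short visit for each subject not yet at month 6, with instruments already used at baseline. The cost of reconciling the crossover timing cannot be sized from the documents.
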